4.1 Inclusion Criteria

Patients who meet all the following conditions are eligible for enrollment.

- 1) Patients with corneal stromal defects, including those caused by trauma or following lesion excision for infection, with a residual stromal thickness of ≥ 300 μm in the defect area.
- 2) Patients aged 18 to 85 years (inclusive, either sex) at the time of consent.
- 3) Patients who are capable of providing written informed consent voluntarily to participate in the study.

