7.4.2 Corneal Findings

Method: Slit-lamp microscopy was used to observe corneal epithelial healing time, corneal clarity (degree of corneal opacity), corneal stromal inflammation, and infection of the surgical eye. Corneal opacity was clinically graded from 0 to 4 (0 = completely transparent; 1 = slight opacity, not easily detectable under direct illumination; 2 = mild opacity, visible on slit-lamp examination; 3 = moderate opacity, partially obscuring the iris; 4 = severe opacity, concealing intraocular structural details).

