8.4.2 Expected harms

8.4.2.1 Hydrogel detachment or displacement

Judgment criteria: Hydrogel displacement or absence in the graft area observed on slit-lamp examination.

Management method: The principal investigator and physicians performing regenerative medicine will discuss the treatment plan during the observation period.

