10.1 Safety Evaluation Items

The primary safety evaluation item: [All adverse events including systemic symptoms].

The secondary safety evaluation items: [Adverse events caused by hydrogel filling] and [Adverse events caused by surgical procedures], which mainly include elevated intraocular pressure, ocular surface inflammatory reaction, hydrogel displacement or detachment, corneal infection, delayed corneal epithelial healing, and decreased corneal endothelial morphology and density, with the judgment criteria

determined by the investigator.

Primary Outcome Measures and Judgment Criteria:

Delayed corneal epithelial healing

Judgment criteria: Corneal epithelium remains unhealed for 7 consecutive days as specified in 7.4.2. If delayed healing is observed during follow-up, timely adjustment of medication is required.

Infection

Judgment criteria:

- ① Severe conjunctival hyperemia accompanied by ciliary hyperemia and purulent discharge as per 7.4.1 (Conjunctival findings);
- ② Corneal infiltration and decreased corneal clarity in the hydrogel-filled area as per 7.4.2 (Corneal findings).

Infection is diagnosed when either ①+② or ② alone is present.

Hydrogel detachment

Judgment criteria:

- ① Depression in the hydrogel-filled area as observed under 7.4.2 (Corneal findings);
- ② Decreased thickness of the hydrogel-filled area detected by corneal OCT (7.3.3);
- ③ Decreased corneal thickness in the hydrogel-filled area detected by corneal topography (7.3.4).

Hydrogel detachment is diagnosed when ① and/or ② and/or ③ is present.

Furthermore, considering the occurrence of side effects and abnormal changes in clinical laboratory values during this clinical study, the overall safety of each subject will be graded into the following four categories:

- ① **Safe:** No side effects or abnormal changes in clinical laboratory values during the study period.
- ② **Basically safe:** Mild study-related side effects occurred during the study period (relieved/resolved without special treatment), or clinically insignificant abnormal changes in clinical laboratory values occurred (resolved upon re-examination without

intervention).

③ **Safety concerns:** Moderate study-related side effects occurred during the study period (relieved/resolved only after symptomatic treatment), or clinically significant abnormal changes in clinical laboratory values occurred (requiring intervention/re-examination monitoring).

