10.2 Efficacy Evaluation Items

Corneal Thickness

Judgment method: At each visit, based on the corneal thickness examination results described in 7.3.3, a corneal thickness improvement effect is considered present when the thickness reduction in the filled defect area does not exceed 20%.

Evaluation method:

① Effective: The improvement effect is observed at least once before Visit 4 and in a total of two or more visits including the final assessment.

② Ineffective: All cases other than ①.

Corneal Clarity (Degree of Corneal Opacity)

Judgment method: At each visit, based on the slit-lamp examination findings of the cornea described in 7.4.2, corneal clarity is considered good (stromal transparency after repair) when the corneal opacity score is ≤ 2 .

Evaluation method:

- ① Effective: Good corneal clarity is observed at least once before Visit 4 and in a total of two or more visits including the final assessment.
- ② Suggestive effective: Corneal thickness improvement effect is observed at least once before Visit 4, but corneal clarity is judged as poor at the final assessment.
- ③ Ineffective: All cases other than ① and ②.

Visual Acuity and/or Corrected Visual Acuity

Judgment method: At each visit, based on the visual acuity examination results described in 7.3.1, using distance decimal visual acuity, a visual acuity improvement effect is considered present when the visual acuity improves by at least one grade compared with the baseline (preoperative) assessment.

Evaluation method:

- ① Effective: The improvement effect is observed at least once before Visit 4 and in a total of two or more visits including the final assessment.
- ② Ineffective: All cases other than ①.

Judgment when "Insufficient Therapeutic Effect"

Judgment method: When at the final assessment, hydrogel degradation exceeds 20%, corneal opacity score is ≥ 3 , and visual acuity is lower than baseline (preoperative visual acuity), the outcome is defined as "insufficient therapeutic effect."

11. Statistical Matters

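### The Section 10.1 rule for hydrogel detachment does not separate gel from host stroma, so thinning of the residual bed under an adherent gel would be counted as detachment

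*Protocol*

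**What the plan says.** Entry depends on the patient's own tissue. Section 4.1 admits "Patients with corneal stromal defects, including those caused by trauma or following lesion excision for infection, with a residual stromal thickness of" at least 300 µm in the defect area, and the Protocol Summary excludes perforation. This is the only place where the residual bed has a figure of its own.

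Section 10.1 gives three signs of detachment:

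- ① "Depression in the hydrogel-filled area as observed under 7.4.2 (Corneal findings"), a slit-lamp sign;
- ② "Decreased thickness of the hydrogel-filled area detected by corneal OCT (7.3.3");
- ③ "Decreased corneal thickness in the hydrogel-filled area detected by corneal topography (7.3.4").

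The combination rule is "Hydrogel detachment is diagnosed when ① and/or ② and/or ③ is present". None of the three has a size limit or a reference visit.

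Section 8.4.2.1 judges the same event differently: "Hydrogel displacement or absence in the graft area observed on slit-lamp examination". It uses no thickness reading.

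Section 7.3.3 asks the OCT for adhesion, filling, and the thickness and clarity of the repaired area. Section 7.4.2 lists the slit-lamp observations as "corneal epithelial healing time, corneal clarity (degree of corneal opacity), corneal stromal inflammation, and infection of the surgical eye". In Section 10.2, "a corneal thickness improvement effect is considered present when the thickness reduction in the filled defect area does not exceed 20" per cent. Stromal thinning, melting and perforation are not named among the evaluation items (3.3.1), the expected harms (8.4.2), the expected adverse events (9.2.2) or the safety items of 10.1.

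**The concern.** Two different harms can lower thickness in the filled area. The product may come loose or dissolve, or the host stroma beneath it may thin. The first concerns how well the gel adheres; the second concerns the tissue that made the eye eligible. A rule that turns any fall in corneal thickness into detachment combines the two under the product's name.

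Safety is the primary objective (Section 2.1), and Section 1 says that no clinical safety reports exist for injectable corneal hydrogels. With 30 subjects, each relabelled subject moves an event rate by 1/30, or 3.3 percentage points. A few such cases would overstate detachment and understate loss of host tissue. A later analysis cannot separate them if the two layers were never read separately.

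**Working it through.** The plan gives no figure to reproduce here. The check compares the rules and then adds a short illustration.

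**Step 1: apply the rules to one eye.** Take an eye whose gel is adherent and unchanged while the bed beneath it thins.

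- Criterion ③: corneal thickness in the filled area is bed plus gel. The bed falls and the gel is stable, so the sum falls and the criterion is met. By the and/or rule it is enough alone.
- Criterion ①: if the surface sinks, a depression is seen. It does not show which layer was lost.
- Criterion ②: thickness of the filled area may mean the gel layer or the total. Read as the total, it is met; read as the gel layer, it is not.
- Section 8.4.2.1: the gel has neither moved nor gone, so there is no detachment.

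The same eye is detached under 10.1 and not detached under 8.4.2.1. No assumed number is needed for this.

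**Step 2: check when the readings are taken.** OCT is scheduled at discharge (6.1.6) and at Weeks 1, 4 and 8 (6.2.1); postoperative day 1 has none (6.1.5). Topography is scheduled at discharge and Weeks 1 and 4, so at Week 8 the scheduled readings serve only ① and ②. Criterion ③ also cites Section 7.3.4 for thickness, while 7.3.4 names only curvature and morphology. These sections need to be reconciled.

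**Step 3: illustrate the size.**

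- Bed: 300 µm, the entry limit in Section 4.1.
- Total thickness after filling: assumed 550 µm, range 500-600 µm. The protocol gives no gel or post-filling thickness.
- Bed loss: 60 µm, chosen for illustration, leaving 300 − 60 = 240 µm, below the entry figure.

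Fall in total thickness = bed loss / total:

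| Assumed total (µm) | Calculation | Fall |
|---|---|---|
| 500 | 60/500 | 12.0% |
| 550 | 60/550 | 10.9% |
| 600 | 60/600 | 10.0% |

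Section 10.1 has no size limit, so each row is coded as detachment. If the 20% limit in 10.2 refers to total thickness, each row also counts as improvement, because 10-12% is below 20%. If the limit refers to the gel layer, these percentages do not bear on 10.2.

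**The case against.** The strongest reply is that bed loss is not invisible to this protocol. The primary safety item in 10.1 is all adverse events. Section 9.1 defines these broadly, and 9.2 covers the time from enrollment to the end of the study. The ophthalmic list in 10.1 is introduced as the main items, so it is not closed. Slit-lamp examination takes place at every visit, and ulceration or infiltration is covered by the infection criteria. This stands. A reader might infer that host-tissue loss would go unreported, or that the safety objective cannot be met. The documents do not support that: once recognised, thinning or perforation is reportable. What remains is that nothing prompts its recognition, and when thickness falls, 10.1 supplies a different diagnosis.

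A reader might also infer that all the detachment signs measure total thickness. They do not: ① is a surface sign and ② is ambiguous. Only ③ plainly refers to corneal thickness, although it is sufficient alone.

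A third tempting inference is that a third or more of the bed could be lost while the eye scores as improved (0.20 × 500 = 100 µm, and 100/300 = 33%; 0.20 × 600 = 120 µm, and 120/300 = 40%). That needs an assumed total thickness, a total-thickness reading of the 20% limit, and no gel loss at all. Section 10.2 later speaks of hydrogel degradation above 20%, so the limit may concern the gel. The figure should not be relied on.

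Finally, reading instructions may sit in the separate operating procedures mentioned in 12.7, which are not shown. They could specify layer readings, but they would not remove the conflict between 10.1 and 8.4.2.1.

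**Conclusion.** The point holds as a misclassification in a stated outcome rule. Under 10.1, thinning of the host bed beneath an adherent gel is counted as detachment through criterion ③, through ① if a depression forms, and possibly through ②. Section 8.4.2.1 would not count it. Residual stromal thickness is used for entry and then not followed as a safety item, so its loss is misclassified or depends on an investigator reporting it unprompted.

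The conflict between the two definitions rests on the text alone. The size does not. The 10-12% fall assumes a 300 µm bed, a 60 µm loss, an unchanged gel and a total of 500-600 µm, and its clash with 10.2 holds only if the 20% limit means total thickness. How often this would happen among 30 subjects cannot be derived from the documents. In an exploratory, descriptive study this is a worthwhile, inexpensive correction and does not make the design unsound.

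**What to change.** - On the OCT scans already scheduled (discharge, Weeks 1, 4 and 8), record gel-layer thickness and residual-bed thickness in the filled area as two separate values. Where the interface is not visible, record the eye as not measurable.
- Reconcile 10.1 with 8.4.2.1 so that detachment rests on the gel layer or its position. State what ② measures, and reconcile ③ with 7.3.4.
- Add residual bed thinning or perforation as a separate descriptive ophthalmic safety item. Report the change in bed thickness from the first post-filling OCT, which is a better reference than the preoperative scan because debridement at surgery (3.4) changes the bed. The number of eyes below 300 µm may be added as description only.

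This defines an outcome and implies no management rule. The cost is two caliper readings instead of one on existing scans, added case report form entries and a wording change in 10.1. There are two limits. Some interfaces will not be measurable, and the first post-filling OCT is at discharge, which has no fixed day, so bed loss before then would not be captured.

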3.3 Evaluation Items

3.3.1 Primary Evaluation Items: Safety Evaluation Items

① Safety Evaluation Items (Systemic)

To evaluate the type, severity, and frequency of all related adverse events.

② Safety Evaluation Items (Ophthalmic)

- Intraocular pressure (IOP)
- Ocular surface inflammatory reaction
- Infection
- Corneal endothelial morphology and density

- Corneal epithelial healing time
- Hydrogel displacement or detachment

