6.1.6 Discharge Date

1) Subjects will undergo ophthalmic examinations including uncorrected and corrected visual acuity, slit-lamp microscopy (anterior segment photography), intraocular pressure, corneal OCT/panoramic OCT, corneal topography, and biomechanical assessment.

2) The investigator will record the subject's ocular status (inflammatory reaction, corneal epithelial healing time, hydrogel adherence) and the presence or absence of adverse events, with detailed documentation in the

electronic medical record.

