6.2 Observation Period: Visits 1~4 (Week 1~Week 8)

6.2.1 Visits 1 (Week 1), Visits 2 (Week 2), 3 (Week 4), 4 (Week 8)

Within each visit window, the following assessments and evaluations will be performed:

- 1) The investigator will inquire about the subject's symptoms and signs since the last visit and the occurrence of any adverse events, with detailed documentation in the electronic medical record.
- 2) Subjects will undergo ophthalmic examinations including: visual acuity (uncorrected and/or corrected), slit-lamp examination (anterior segment photography), intraocular pressure measurement, corneal OCT + panoramic OCT (weeks 1, 4, and 8), B-scan ultrasonography (week 2), confocal microscopy (weeks 4 and 8), corneal topography (weeks 1 and 4), biomechanical assessment (weeks 1 and 4), and fundus photography (week 4).

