7.3.3 Corneal Shape Analysis

Method: Anterior segment OCT of the surgical eye to evaluate hydrogel adhesion and filling, as well as the thickness and corneal clarity of the repaired area.

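### The detachment rule in 10.1 leaves out the gel-to-bed adhesion that the OCT is meant to evaluate, so a gel that separates without depression or thinning is not counted.

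*Protocol*

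**What the plan says.** Section 3.3.1 of the protocol lists "Hydrogel displacement or detachment" among the ophthalmic safety items, which are the primary evaluation items. Section 10.1 then gives the judgment criteria for detachment. Criterion ① is a sunken surface over the filled area at the slit lamp. Criterion ② is worded "Decreased thickness of the hydrogel-filled area detected by corneal OCT (7.3.3". Criterion ③ is a thinner cornea over the filled area on topography. The combination rule is that any one sign is enough: "Hydrogel detachment is diagnosed when ① and/or ② and/or ③ is present".

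Three other places bear on the same outcome.

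- Section 7.3.3, which criterion ② cites, describes the examination as "Anterior segment OCT of the surgical eye to evaluate hydrogel adhesion and filling", together with thickness and clarity of the repaired area.
- Section 6.1.6 has the investigator record the ocular status at discharge, in these terms: "inflammatory reaction, corneal epithelial healing time, hydrogel adherence". OCT is also done at discharge, and section 6.2 schedules "corneal OCT + panoramic OCT (weeks 1, 4, and 8".
- Section 8.4.2.1 has its own criterion for detachment or displacement: the gel is seen on slit lamp to be displaced or absent. It does not define displacement.

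**The concern.** Detachment of a sutureless gel is, in plain terms, loss of contact with the bed. The three signs in 10.1 are signs of lost, thinned or sunken material. They overlap with loss of contact but are not the same thing. The protocol plans to look at adhesion, on OCT and in the discharge record, yet the written rule for the outcome that depends most on adhesion does not use it. From the 7.3.3 examination it takes thickness only.

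What is at stake is the meaning of a named item under the primary safety objective. A reader of the final report would take the detachment count as the number of gels that came away from the bed. Under 10.1 it is the number of eyes with a depression or any thinning. The two can differ in either direction.

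**Working it through.** The plan states no detachment rate and makes no calculation from one, so there is no figure to reproduce. The check applies the written rules to four kinds of eye. The inputs are criteria ① to ③ and the any-one rule (10.1), the slit-lamp rule (8.4.2.1), and the thickness rule in 10.2, under which a reduction of no more than 20% in the filled area counts as an improvement effect at that visit.

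| Eye | ① depression | ② OCT thinning | ③ topography thinning | 10.1 result | 8.4.2.1 result |
|---|---|---|---|---|---|
| A. Gel lost from the defect | yes | yes | yes | detached | met (absent) |
| B. Gel separated, and sunken or thinned | at least one of ① to ③ | – | – | detached | depends on how displacement is read |
| C. Gel separated, no depression, no thinning | no | no | no | **not detached** | not clearly met |
| D. Gel fully adherent, some thinning of at most 20% | no | yes | yes or no | **detached** | not met |

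Eyes A and B are classified as one would want. Eye C is the gap: its contact with the bed is lost and no criterion responds. Under 10.2, eye C also passes the thickness rule at that visit, because its thickness has not fallen. Eye D is the opposite error: contact is intact, but criterion ② has no threshold, so any decrease counts. The same eye shows an improvement effect on thickness under 10.2.

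Whether a given separated gel falls in row B or row C depends partly on how thickness is measured. Neither 7.3.3 nor 10.1 says whether the OCT thickness is that of the gel alone or the full distance from surface to bed, including any gap. If it is the full distance, a gap would leave the value unchanged or raise it. If it is the gel alone, a separated gel of unchanged thickness still gives no decrease. Row C can arise under either reading.

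The effect on the rate follows directly. Let c be the number of eyes in row C and d the number in row D, and assume that all 30 planned subjects are treated and assessed. Then

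error in the detachment rate = (d − c) / 30.

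The documents give neither c nor d. For a range of assumed values:

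- c = 1, d = 0: −1/30 = −3.3 percentage points
- c = 2, d = 0: −2/30 = −6.7 points
- c = 2, d = 2: 0, with two eyes misclassified each way
- c = 0, d = 2: +2/30 = +6.7 points

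For scale, take two eyes in row A, two in row C and none in row D (assumed). The report would show 2/30 = 6.7% (exact 95% interval 0.8% to 22.1%), while loss of contact occurred in 4/30 = 13.3% (3.8% to 30.7%). This shows what a given number of missed eyes would do. It is not an estimate of how many there will be.

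**The case against.** A reader might infer that any gel that lifts off the bed is scored as not detached. The documents do not support that. A lifted gel that also sinks or thins meets at least one criterion, and because ② and ③ have no threshold, slight thinning is enough. Only the eye with no depression and no thinning is missed.

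A reader might also infer that the detachment rate is biased downward. That does not follow either. Row D is as much a consequence of the written rule as row C, and nothing in the protocol says which would be more common.

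Three further points on the other side have weight. First, displacement in 8.4.2.1 is undefined, and an investigator could read a gel lifted at its edge as displaced, so one can say only that the case is not clearly covered there. Second, the primary safety item in 10.1 is all adverse events, 9.1 defines these broadly, and 10.1 leaves judgment criteria for the secondary safety items to the investigator. A separated gel can therefore still be reported as an adverse event; what misses it is the detachment count. Third, adhesion is assessed more often than the discharge record alone suggests, since the 7.3.3 OCT is repeated at weeks 1, 4 and 8, and section 3.4 adds a slit-lamp check of gel integrity on day 1. The case report form is not shown, so it may already hold an adhesion field.

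The study is also exploratory, single-arm and descriptive, and no test or decision threshold rests on the detachment rate. That limits the consequences. It does not remove the omission: the protocol prints a specific detachment rule, and that rule does not use adhesion.

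**Conclusion.** The point holds in a limited form. The rule in 10.1 does not use an adhesion finding that 7.3.3 says the OCT is done to obtain. A gel separated from the bed without depression or thinning is therefore not counted as detached, and 8.4.2.1 does not clearly catch it. Each such eye is worth 3.3 percentage points in a study of 30. How often this would happen is unknown, and because the same rule counts any thinning as detachment, the net direction of bias in the reported rate is unknown too. The conclusion that the rule omits adhesion rests on the text alone; the sizes rest on assumed counts and on all 30 subjects being assessed. The change is worth making before enrolment because it is cheap and concerns a named safety item.

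**What to change.** Four changes to outcome measurement, none of which touches treatment:

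1. In 10.1, add loss of hydrogel-to-bed contact on the 7.3.3 OCT as a detachment criterion, with the extent that counts fixed in advance by the investigators. Without a stated extent, a trivial focal gap would count as detachment, and the new criterion would repeat the missing-threshold problem of ② and ③.
2. Record adhesion as complete, partly lost or lost at discharge and at the scheduled OCTs (weeks 1, 4 and 8).
3. Report partial loss of adhesion and complete loss of adhesion separately from thinning alone, so that rows C and D can be told apart.
4. Reconcile the definitions in 8.4.2.1 and 10.1, including what displacement means, so that one eye cannot be classified differently under the two sections.

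The cost is one added criterion and one extra field on the case report form (if it is not already there), read from scans already scheduled. The reported detachment rate may turn out less favourable.
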